7.3 Informed Consent

Prior to undergoing any study-specific tests or procedures, the subject or their legally authorized representative must sign and date the site's current and approved Institutional Review Board (IRB)/Ethics Committee (EC) informed consent form (ICF) in order to be eligible for study participation. The informed consent must contain all elements required by 21 CFR Part 50 and ISO 14155:2011/ AC: 2011 and comply with the ethical principles of the Declaration of Helsinki.

7.3.1 Process for Obtaining Informed Consent

The process for obtaining informed consent is outlined below:

- The Investigator or his/her authorized designee conducts the informed consent process,
- All aspects of the clinical study that are relevant to the subject's decision to participate will be included in the consent form,
- Investigators will avoid any coercion or undue improper influence on, or inducement of, the subject to participate,
- The consent process shall not waive or appear to waive the subject's legal rights,
- The consent must use native non-technical language that is understandable to the subject,
- The Investigator or designee will provide ample time for the subject to read and understand the informed consent form and to consider participation in the clinical investigation,
- The consent must include personally dated signatures of the subject and the Investigator, or an authorized designee responsible for conducting the informed consent process, and/or all signatures required by the reviewing IRB/EC,
- The Investigator or designee will provide the subject with a copy of the signed and dated informed consent form and any other written information.

7.3.2 Subjects Needing Legally Authorized Representative

Informed consent may be given by a legally authorized representative only if a subject is unable to make the decision to participate in a clinical study. In such cases, the subject shall also be informed about the clinical study within his/her ability to understand.

Please follow the local IRB/EC guidelines on this process.

	No.: CP 64007	REV. D
	TITLE: Disrupt PAD+ Study	
	CLASS: CLINICAL PROTOCOL	PAGE 18 OF 57

7.3.3 Subjects Unable to Read or Write

Informed consent shall be obtained through a supervised oral process if a subject or legally authorized representative is unable to read or write, if allowed by the IRB/EC. An independent witness shall be present throughout the process. The written informed consent form and any other information shall be explained to the prospective subject or his/her legally authorized representative and, whenever possible, either shall sign and personally date the informed consent form. The witness also signs and personally dates the informed consent form attesting that the information was accurately explained and that informed consent was freely given.

7.3.4 Addition of New Information

Shockwave Medical will revise the written informed consent form whenever new information becomes available that may be relevant to the subject's confirmed participation in the study. The revised information will be sent to the Investigator for approval by the IRB/EC. After approval by the IRB/EC, a copy of this information must be provided to the participating subjects, and the informed consent process as described above needs to be repeated.

Please follow the local IRB/EC guidelines on the process of re-consenting subjects.

	No.: CP 64007	REV. D
	TITLE: Disrupt PAD+ Study	
	CLASS: CLINICAL PROTOCOL	PAGE 19 OF 57

7.4 Schedule of Events and Evaluations

Table 1 lists the schedule of events and evaluations required for the study.

Table 1. Study Schedule of Events

	Screening/ Baseline ²	Enrollment and Procedure	Discharge ³	30 Days ⁴ (+/- 7 days)	6 Months ⁴ (+/- 30 days)	12 Months (+/- 30 days)	Pre-Target Limb Revasc
Informed Consent	X ¹						
Medical History	X						
Physical Examination	X		X	X	X	X	X
Baseline labs	X						
Pregnancy test	X						
Ankle Brachial Index (ABI)	X			X ⁵	X ⁵	X	X
Rutherford Category (RC)	X			X	X	X	X
Angiographic Lesion Assessment		X					X
IVL Procedure		X					
Duplex Ultrasound						X	
Medication regimen per protocol			X	X	X	X	X
Adverse Event Assessment		X	X	X	X	X	X
OCT or IVUS (optional)		X					

¹ Consent to be obtained within 30 days prior to procedure.

² Evaluations may be done up to 30 days before the procedure with the exception of ABI, which may be completed within 60 days of the procedure.

³ Examinations are to be completed within 12-24 hours post-procedure or prior to discharge, whichever comes first.

⁴ 30-Day and 6-month visit can be conducted as an on-site or remote visit.

⁵ ABI should be assessed if visit is conducted on-site.

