5.2 Secondary Endpoint(s)

Performance

- IVL Technical success is defined as residual stenosis $\leq 30\%$ without flow-limiting dissection (\geq Grade D) of the lesion post-IVL by angiographic core lab.
- Procedural success is defined as final residual stenosis $\leq 30\%$ without any flow-limiting dissection (\geq Grade D) in all target lesions by angiographic core lab.

Safety

- MAE at 6 and 12 months

Patency

- Primary patency at 12 months defined as freedom from clinically-driven target lesion revascularization (TLR) and freedom from restenosis determined by duplex ultrasound or angiogram $\geq 50\%$ stenosis. Acute PTA failure requiring a stent of the target lesion at any time during the index procedure will be counted as a loss of primary patency.
- Clinically driven target lesion revascularization (TLR) at 30 days, 6 and 12 months

Clinical

- Ankle-brachial index (ABI) at 12 months, reported as change from baseline
- Rutherford Category at 30 days, 6 and 12 months, reported as change from baseline

	No.: CP 64007	REV. D
	TITLE: Disrupt PAD+ Study	
	CLASS: CLINICAL PROTOCOL	PAGE 14 OF 57

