7.2.2 Exclusion Criteria

General Exclusion Criteria

1. Rutherford Clinical Category 0, 1 and 6.
2. Subject has active infection requiring antibiotic therapy.
3. History of endovascular or surgical procedure on the target limb within the last 30 days or planned within 30 days of the index procedure. *Note: Concomitant IVL treatment to facilitate large bore access at the time of procedure is allowed.*
4. Subject in whom antiplatelet or anticoagulant therapy is contraindicated.
5. Subject has known allergy to contrast agents or medications used to perform endovascular intervention that cannot be adequately pre-treated.
6. Subject has known allergy to urethane, nylon, or silicone.
7. Myocardial infarction within 60 days prior to enrollment.
8. History of stroke within 60 days prior to enrollment.
9. Subject has acute or chronic renal disease defined as serum creatinine of > 2.5 mg/dL or > 220 $\mu\text{mol/L}$, unless on dialysis.
10. Subject is pregnant or nursing.
11. Subject is participating in another research study involving an investigational agent (pharmaceutical, biologic, or medical device) that has not reached the primary endpoint.
12. Subject has other medical, social or psychological problems that, in the opinion of the investigator, preclude them from receiving this treatment, and the procedures and evaluations pre- and post-treatment.
13. The planned use of specialty balloons, re-entry or atherectomy devices in the target lesion(s).

Angiographic Exclusion Criteria

14. In-stent restenosis within 10mm of the target zone.
15. Target lesions distal to the popliteal artery.
16. Evidence of aneurysm or thrombus in target vessel.
17. No calcium or mild calcium in the target lesion.
18. Target lesion within native or synthetic vessel grafts.

	No.: CP 64007	REV. D
	TITLE: Disrupt PAD+ Study	
	CLASS: CLINICAL PROTOCOL	PAGE 17 OF 57

19. Subject has more than three target lesions requiring treatment.

20. Subject has significant non-target lesion (>50% stenosis or occlusion) within the target limb (e.g. iliac, common femoral or below-the-knee) not successfully treated prior to treatment of the target lesions.

21. Failure to successfully cross the guidewire across the target lesion; successful crossing defined as tip of the guidewire distal to the target lesion in the absence of flow limiting dissections or perforations.

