7.6 Screening/Baseline Procedures

Baseline assessments must be completed within 30 days of the procedure with the exception of ABI, which can be completed within 60 days of the procedure, and a pregnancy test, which must be done within 7 days of procedure. Informed consent must be obtained prior to any study-specific evaluations needed to assess eligibility which are not considered standard of care. Subjects on warfarin or direct thrombin inhibitors should be followed per institutional standard of care by the physician.

Baseline assessments include:

- Medical history
- Physical examination
 - Vital signs
 - Height and weight
- Ankle-brachial index
- Rutherford Category
- Laboratory assessments
- Urine pregnancy test if female of child-bearing age

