7.7.2 Index Procedure

Non-target lesions within a limb should be treated successfully prior to treatment of any target lesions. Non-target lesions may be treated with any commercially available device; treating a non-target lesion with a device that is unapproved or considered investigational will result in a protocol deviation.

A full description of the procedure is detailed in the Instructions for Use (IFU). The appropriately sized IVL balloon catheter should be selected per the IFU (select a balloon catheter size that is 1.1:1 based on balloon compliance chart and reference vessel diameter; the largest diameter

	No.: CP 64007	REV. D
	TITLE: Disrupt PAD+ Study	
	CLASS: CLINICAL PROTOCOL	PAGE 21 OF 57

balloon should be used if 1.1:1 sizing is not available). Once the IVL balloon is placed in the target lesion area, the balloon should be inflated to 4 atm and IVL treatment delivered for the pre-programmed time of 15 seconds to deliver 30 pulses. Note that the generator is programmed to force a minimum pause time of 10 seconds following every 30 pulses delivered. **Table 2** lists the pulsing sequence for IVL treatment.

Table 2: IVL System Sequence Chart

Treatment Frequency	2 Hz (1 Pulse every 0.5 Seconds)
Maximum Number of Continuous Pulses (1 cycle)	30 Pulses
Minimum Pause Time	10 Seconds
Maximum Total Pulses Per Catheter (10 cycles)	Displayed on generator

If the operator is unable to pass the IVL balloon through the lesion, a standard PTA balloon up to 3.0mm may be used for pre-dilatation prior to treatment with the IVL Balloon. All efforts should be made to pass the IVL balloon prior to use of a standard PTA balloon.

Following delivery of the first IVL cycle (30 pulses), inflate the balloon to the reference size using the Balloon Compliance Chart (refer to IFU) and record lesion response on fluoroscopy. Deflate the balloon and wait 10 seconds to re-establish blood flow. Repeat the steps above to complete a second delivery cycle of 30 pulses to complete a single treatment consisting of 60 pulses. Additional treatment cycles can be performed if deemed necessary.

If an additional lesion area needs to be treated, follow the treatment steps as identified per the IFU. The catheter can be advanced to the next treatment area. Confirm the balloon catheter is of the appropriate size for the next treatment area.

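### Treating another lesion in the same limb can enter the reported ABI change through the 60-day baseline window and, when done in the index session, both the ABI and the Rutherford change

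*Combined protocol and SAP*

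**What the plan says.** - **Endpoints.** Section 5.2 lists two clinical secondary endpoints: "Ankle-brachial index (ABI) at 12 months, reported as change from baseline" and "Rutherford Category at 30 days, 6 and 12 months, reported as change from baseline".
- **Baseline windows.** Table 1, footnote 2 (section 7.4) allows evaluations up to 30 days before the procedure, "with the exception of ABI, which may be completed within 60 days of the procedure". Section 7.6 agrees: "Baseline assessments must be completed within 30 days of the procedure with the exception of ABI, which can be completed within 60 days". Rutherford Category is a baseline assessment and falls under the 30-day limit.
- **Limb washout.** Exclusion 3 (section 7.2.2) reads: "History of endovascular or surgical procedure on the target limb within the last 30 days or planned within 30 days of the index procedure". A note allows concomitant IVL for large-bore access. The date from which the last 30 days are counted is not given.
- **Non-target lesions.** Exclusion 20 rules out a limb with a non-target lesion above 50% stenosis that is "not successfully treated prior to treatment of the target lesions". Section 7.7.2 adds: "Non-target lesions within a limb should be treated successfully prior to treatment of any target lesions". It also says: "Non-target lesions may be treated with any commercially available device".
- **Analysis.** Section 9.1 is descriptive, with a paired t-test or signed-rank test for within-subject change and p-values without multiplicity correction. It describes no split or adjustment for non-target treatment. Table 1 schedules no ABI or Rutherford reading between non-target treatment and IVL.

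**The concern.** A change from baseline measures whatever happened to the limb between the two readings. If another lesion in that limb is revascularized after the baseline reading, its benefit is counted with that of the target-lesion treatment. The expected direction is favourable, because a successful non-target procedure should raise ABI and ease symptoms. With no control arm, nothing in the data would show it.

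This can happen by two independent routes.

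- **Route (a), ABI only.** The ABI window is twice as long as the limb washout, so an earlier staged procedure can fall between the baseline ABI and the index procedure.
- **Route (b), ABI and Rutherford.** Non-target lesions treated in the index session come after both baselines, whatever the length of the windows.

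At stake is the reading of the two endpoints that section 5.2 lists as clinical. Section 12.9 foresees use of the study data in publications, regulatory submissions and marketing.

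**Working it through.** The plan gives no figure on this point, so the check sets its time windows side by side. Day 0 is the index procedure.

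**Route (a): inputs**
- Baseline ABI taken on day -a, with a from 0 to 60 (7.4, 7.6).
- Baseline Rutherford taken on day -r, with r from 0 to 30 (7.6).
- Earlier target-limb procedure on day -d, with d of 31 or more, if the washout runs back from day 0 (exclusion 3).
- A limb is exposed when the baseline reading falls on or before the procedure day.

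**Route (a): result**
- ABI: a ≥ d with a ≤ 60 and d ≥ 31 is possible for d = 31 to 60. That is 60 - 30 = 30 exposed days.
- Rutherford: r ≥ d would need r ≥ 31, but r ≤ 30. That is 0 exposed days.
- Example: ABI on day -58, a permitted procedure on that limb on day -40, IVL on day 0. The day -58 reading is a valid baseline, and the 12-month change includes the day -40 procedure.

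**Sensitivity to the unstated anchor.** If the washout runs back from a screening date s days before the procedure (s from 0 to 30), the exposed days are 60 - (30 + s) = 30 - s. This gives 30 days for s = 0, 15 for s = 15 and 0 for s = 30.

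**Origin of the older ABI.** Table 1, footnote 1 places consent within 30 days before the procedure. An ABI from days -60 to -31 therefore predates consent and has to be a standard-of-care reading. It could come from the work-up for the earlier procedure.

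**Route (b).** Non-target treatment in the index session happens on day 0, before IVL. Both baselines precede it, even if taken the day before. Shortening the ABI window would not change this.

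**Size (illustration; none of these values is in the documents).** Let f be the share of limbs with non-target treatment after baseline, by either route, and g the mean ABI gain from it still present at 12 months. The contribution to the mean ABI change is f × g.

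| f | g | f × g |
|---|---|---|
| 0.10 | 0.05 | 0.005 |
| 0.25 | 0.10 | 0.025 |
| 0.50 | 0.20 | 0.10 |

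A different choice, f from 0.10 to 0.30 and g from 0.15 to 0.30, gives 0.015 to 0.09, inside the same range.

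For the middle row, assume 40 paired readings and an SD of change of 0.15 to 0.25. The standard error is SD/√40 = 0.024 to 0.040. With no effect of the target-lesion treatment, a two-sided 5% test (normal approximation) would then reject about 18% (SD 0.15) or 10% (SD 0.25) of the time. Over the whole grid this rate runs from about 5% to 99%, so the assumptions decide the answer.

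**The case against.** The strongest reply is that this is a narrow issue in descriptive secondary summaries. Route (a) needs a staged procedure in one particular month, an ABI taken before it, and that older ABI kept as baseline. It also depends on how exclusion 3 is anchored. The plan never says that the ABI or Rutherford change is the effect of IVL. Section 7.7.2 also allows post-dilatation, drug-coated balloons and provisional stents at the target lesion. Clinically-driven TLR is a further secondary endpoint that reflects clinical status, and the primary endpoints use neither ABI nor Rutherford.

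Most of this stands and limits the weight of the point. It does not remove it. The rules, followed as written, permit the sequence, and no provision detects or separates it. Adjunctive balloons and stents belong to the target-lesion strategy, whereas non-target treatment adds gain from a different lesion.

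A reader might infer more than the documents support:
- *That the 60/30-day mismatch also affects Rutherford.* It does not: the 30-day Rutherford window leaves no exposed day.
- *That the mismatch causes the same-session effect.* It does not: that effect would exist with any baseline.
- *That the IVL effect is overstated by a known amount.* The documents do not say how many limbs have non-target treatment or what it adds, and they define no IVL-only ABI or Rutherford effect.
- *That limbs without non-target treatment would isolate IVL.* They would not, because of the permitted adjuncts.

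**Conclusion.** The point holds as a modest improvement to secondary endpoints. Another lesion's benefit can enter the ABI change by route (a), for up to 30 exposed days, if the washout is counted from the index procedure. The exposure shrinks to zero if it is counted from screening 30 days earlier. By route (b) it can enter both the ABI and the Rutherford change, whatever the windows. The expected bias is in one direction, assuming that successful non-target treatment improves both measures. Its size is unknown: 0.005 to 0.10 in mean ABI change is an illustration for both routes together, not an estimate. The reported change reflects IVL plus any adjunctive balloon or stent, so it could not be credited to IVL alone in any case.

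There is also a textual conflict. Exclusion 3 bars target-limb procedures planned within 30 days of the index procedure, and its note excepts only concomitant IVL for large-bore access. Section 7.7.2 provides for treating non-target lesions in the limb before the target lesions. These passages must be reconciled.

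**What to change.** 1. **Sections 7.6 and 7.4 (Table 1, footnote 2).** Accept a baseline ABI only if it was measured after the most recent prior procedure on that limb. Otherwise repeat it before the index procedure. This takes route (a) from 30 exposed days to 0 and leaves route (b) unchanged.
2. **Section 9.1.** Keep the full-cohort summary. Add a supplementary descriptive table of ABI and Rutherford change for limbs with and without non-target treatment between the baseline reading and the end of the index procedure.
3. **Case report forms.** Confirm that they capture non-target treatment and its date. They are a separate attachment, so this cannot be checked from the protocol.
4. **Exclusion 3.** State the date from which the last 30 days are counted, and reconcile the exclusion with section 7.7.2.

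**Cost.** An occasional repeat of a non-invasive test already in the schedule, a few sentences, and one table. The split will be imprecise: there are at most 40 subjects and the subset sizes are unknown. Limbs without non-target treatment may also have less multilevel disease, so the two groups should be described and not compared as if like for like.

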7.5 Medications

Anticoagulation/antiplatelet medications will be administered according to the 2017 European Society of Cardiology (ESC) and European Society of Vascular Surgery (ESVS) PAD guidelines (Aboyans et al., 2018) and the 2016 American College of Cardiology (ACC) and American Heart Association (AHA) PAD guidelines (Gerhard-Herman et al., 2017).

	No.: CP 64007	REV. D
	TITLE: Disrupt PAD+ Study	
	CLASS: CLINICAL PROTOCOL	PAGE 20 OF 57

Additional recommendations for anticoagulation and antiplatelet medications include:

- Unfractionated heparin dosing should be undertaken according to hospital standard of care.
- Prasugrel or ticagrelor may be used as an alternative to clopidogrel for existing management of acute coronary syndrome (ACS).
- Follow antiplatelet and anticoagulation guidelines for the management of patients with atrial fibrillation.

7.6 Screening/Baseline Procedures

Baseline assessments must be completed within 30 days of the procedure with the exception of ABI, which can be completed within 60 days of the procedure, and a pregnancy test, which must be done within 7 days of procedure. Informed consent must be obtained prior to any study-specific evaluations needed to assess eligibility which are not considered standard of care. Subjects on warfarin or direct thrombin inhibitors should be followed per institutional standard of care by the physician.

Baseline assessments include:

- Medical history
- Physical examination
 - Vital signs
 - Height and weight
- Ankle-brachial index
- Rutherford Category
- Laboratory assessments
- Urine pregnancy test if female of child-bearing age

7.7 Index Procedure

7.7.1 Definition of Enrollment

The definition of enrollment is when the subject signs informed consent, meets all inclusion criteria, none of the exclusion criteria, and the IVL catheter has been inserted over a 0.014" guidewire which had been previously passed across the study lesion.

7.7.2 Index Procedure

Non-target lesions within a limb should be treated successfully prior to treatment of any target lesions. Non-target lesions may be treated with any commercially available device; treating a non-target lesion with a device that is unapproved or considered investigational will result in a protocol deviation.

A full description of the procedure is detailed in the Instructions for Use (IFU). The appropriately sized IVL balloon catheter should be selected per the IFU (select a balloon catheter size that is 1.1:1 based on balloon compliance chart and reference vessel diameter; the largest diameter

	No.: CP 64007	REV. D
	TITLE: Disrupt PAD+ Study	
	CLASS: CLINICAL PROTOCOL	PAGE 21 OF 57

balloon should be used if 1.1:1 sizing is not available). Once the IVL balloon is placed in the target lesion area, the balloon should be inflated to 4 atm and IVL treatment delivered for the pre-programmed time of 15 seconds to deliver 30 pulses. Note that the generator is programmed to force a minimum pause time of 10 seconds following every 30 pulses delivered. **Table 2** lists the pulsing sequence for IVL treatment.

Table 2: IVL System Sequence Chart

Treatment Frequency	2 Hz (1 Pulse every 0.5 Seconds)
Maximum Number of Continuous Pulses (1 cycle)	30 Pulses
Minimum Pause Time	10 Seconds
Maximum Total Pulses Per Catheter (10 cycles)	Displayed on generator

If the operator is unable to pass the IVL balloon through the lesion, a standard PTA balloon up to 3.0mm may be used for pre-dilatation prior to treatment with the IVL Balloon. All efforts should be made to pass the IVL balloon prior to use of a standard PTA balloon.

Following delivery of the first IVL cycle (30 pulses), inflate the balloon to the reference size using the Balloon Compliance Chart (refer to IFU) and record lesion response on fluoroscopy. Deflate the balloon and wait 10 seconds to re-establish blood flow. Repeat the steps above to complete a second delivery cycle of 30 pulses to complete a single treatment consisting of 60 pulses. Additional treatment cycles can be performed if deemed necessary.

If an additional lesion area needs to be treated, follow the treatment steps as identified per the IFU. The catheter can be advanced to the next treatment area. Confirm the balloon catheter is of the appropriate size for the next treatment area.

Post-dilatation with a semi or non-compliant PTA balloon catheter should be completed when post-IVL results in one of the following below. The physician should use a 1:1 balloon catheter to artery ratio and may dilate for up to three minutes.

- Residual stenosis $\geq 30\%$ by visual estimate, or
- Presence of a flow-limiting (\geq Grade D) dissection, or
- Trans-lesional gradient >10 mm Hg is observed.

Follow the angiographic core lab guidelines to complete angiography showing all target lesions with reproducible landmarks for follow-up evaluation and assessment.

	No.: CP 64007	REV. D
	TITLE: Disrupt PAD+ Study	
	CLASS: CLINICAL PROTOCOL	PAGE 22 OF 57

Any commercially approved drug-coated balloon may be used after IVL. Provisional stenting should be performed with a bare metal or drug-eluting stent after primary treatment or post-dilatation balloon inflations are determined not to be successful. The angiographic core lab will confirm correct use of a stent based on the criteria above for subjects that receive a provisional stent. A provisional stent should be placed for an acute IVL failure defined as:

- Residual stenosis $\geq 50\%$ by visual estimate, or
- Un-resolved flow-limiting (\geq Grade D) dissection, or
- Trans-lesional gradient >10 mm Hg is observed.

Procedural Imaging Requirements

An angiographic cine image will be obtained for each lesion treated including pre-procedure, post-IVL and end of procedure. All angiographic images must be submitted to the core lab for analysis. Intravascular imaging (including IVUS or OCT) is optional. If performed, images from the three timepoints (pre-procedure, post-IVL and end of procedure) should be submitted to the Study Sponsor for analysis.

